Our team has developed safety procedures to address any physical or mental issues in real-time. Our aim is always to keep participants safe, give them resources they might need, and adhere to timely adverse event classification and reporting (e.g., severe adverse events (SAEs), unanticipated problems (UAPs), and adverse events (AEs)). If the participant endorses self-harm ideation or is in emotional distress (e.g., in session, on the phone with a member of the study staff, via email), staff will follow a mental health protection for human subjects procedures, on which all study staff will be trained. This procedure has been used successfully in a similar study conducted by MPI [name] (NH170001).

All participants will be encouraged to contact the project staff (e.g., project director, an investigator) and their primary care physician regarding any side effects or adverse events that occur. Adverse events impacting participant safety may result in withdrawal from the study intervention.

Participants will be asked about potential adverse events in all self-report surveys. Participants will be asked to report side effects/adverse events related to the interventions by choosing from a list generated from the literature and the investigators' experience (see below). In addition, we will query any new or worsening issues.

Question: Since you started your participation in the study have you experienced any of the following?
Check all that apply.

- Worsening pain
- Increased muscle soreness
- Feeling more upset than usual when something reminded you of the past
- Increased feelings of sadness
- Increased feelings of anxiousness
- Feeling more tired or fatigued than usual
- Feeling more isolated or lonely
- Other physical or mental symptoms (please describe)

Please let us know if you think these symptoms were possibly related to the study

- [Show selected items with yes/no for related to study]
- [If yes] Please explain what happened: _____

Question: Since your survey, have you experienced a NEW or WORSENING medical issue or event which resulted in any of the following?

a. Required you to stay overnight in a hospital?

No

Yes

- When did this occur? _____
- What happened? _____
- Are you still being treated for this?
 - No
 - Yes
- Anything else you want to share about this? _____

b. Experienced a problem that resulted in a severe or permanent disability?

No

Yes

- When did this occur? _____
- What happened? _____

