- Are you still being treated for this?
 - No
 - Yes

- Anything else you want to share about this? _____

c. Experienced a life threatening injury or event?

No

Yes

- When did this occur? _____
- What happened? _____
- Are you still being treated for this?
 - No
 - Yes

Anything else you want to share about this? _____

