5.2.1 Research Participants Protections Against Risks

The expected risks associated with this research have been deemed minimal by the Minneapolis VA IRB. All potential participants will be actively engaged in healthcare; they will have been identified through the electronic record in which they have had at least two visits with a provider in the past year. Also, as part of standard VA policy, Veteran patients complete annual suicidality screening. The project team has developed

plans for risk mitigation that meet or exceed what currently exists within the VA health system. See Table 1 for plans to protect participants against risks and Sections 5 and 6 for monitoring and reporting plans.

As part of the study, we will monitor safety after consent has been secured (e.g. screening, intervention, follow up). Safety concerns may be learned of actively (e.g. through querying at screening or in surveys) or passively (e.g. participant discloses during any communication at any point on Webex, by email or on phone).

All participant facing staff will be trained, certified and monitored by investigators to ensure the satisfactory implementation of safety and monitoring procedures. In the event a staff member learns a participant is at risk of experiencing a serious adverse event (e.g., suicidality) they will implement safety procedures developed by our team's clinical health experts (summarized in Table 1 and detailed in the manual of operations).

MPIs and Co-Investigators will conduct, at least monthly, a review of safety data and meet with project staff to discuss any problems or concerns that arise; additional training to implement risk monitoring, documentation and implementation of safety procedures will occur as necessary.

Table 1. Protection Against Risks

Type of Risk	Risk Mitigation
Confidentiality and Data Safety	
• All staff receive HIPAA and data safety training that includes maintaining the confidentiality and security of research records and information.• Details regarding the protection of study databases and source documentation is provided in sections 8.

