Health Surveys (All)	
• All participants will have the option of skipping any interview or questionnaire questions they do not wish to answer.• All surveys will be prefaced by the following*: "Our first priority is your safety. The following questions relate to your emotional and mental wellbeing. We recognize that sharing this information can be challenging. Please remember while answering these questions to take care of yourself and if you are feeling upset and

	
would like help, please call the Veterans Crisis line by dialing 988 and pressing 1.”
 
• All surveys will have the following message at the end*: “Our first priority is your safety. The previous questions relate to your emotional and mental wellbeing. We recognize that sharing this information can be challenging. Please remember to take care of yourself, and if you are feeling upset and would like help, please call the Veterans Crisis Line by dialing 988 and pressing 1. 
*Language based on suggestions by our Veteran Advisors

Health Surveys (Follow Up Only)	
• All participants will be queried for Serious Adverse Events. “Since your last survey, have you experienced a NEW or WORSENING medical issue or event which resulted in any of the following:
a. Overnight stay in a hospital?” (no, yes with open fields to describe when it occurred, what happened, if still being treated)b. Problem that results in a severe or permanent disability?” (no, yes with open fields to describe when it occurred, what happened, if still being treated)c. A life-threatening injury or event? (no, yes with open fields to describe when it occurred, what happened, if still being treated)

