Screening procedures	
• Potential research participants will undergo baseline screening to ensure they meet eligibility criteria and it is safe for them to participate.• Baseline screening will be conducted by staff applying structured checklists to existing electronic medical records review• Screening staff will be trained and supervised by the clinical psychologist MPI and Co-Is responsible for data collection. The following is considered exclusionary:
• Hospitalization for a severe mental illness-related issue in the past 6 months; active psychotic symptoms, suicidal ideation, or manic episodes; active substance use disorder that is poorly controlled.• Staff will be trained to actively monitor for potential emotional distress during baseline eligibility calls and to implement safety procedures if needed. The manual of operations details steps for assessing the nature of the situation, responding appropriately to ensure participant safety, documenting the event and notifying the Project Director and the MPIs (see Section 6). Participants in which imminent risk for suicidality is possible will be offered a warm handoff to the Veterans Crisis Line; if they decline, or disconnect, staff will immediately 1) contact the local police department to conduct a wellness check, then 2) contact the Veterans Crisis line to report event and 3) contact the participants' local suicide prevention team.

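### The scheduled serious-adverse-event question is ambiguous for psychiatric events, and it is the only scheduled route to them in Usual Care

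*Combined protocol and SAP*

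**What the plan says.** Protocol 3.3.3 sets out two survey questions. The first is a symptom checklist that covers sadness, anxiousness, isolation and being upset by reminders of the past, and ends with "Other physical or mental symptoms (please describe". The second is the serious-event question. Its stem is "have you experienced a NEW or WORSENING medical issue or event which resulted in any of the following", followed by three branches: "Required you to stay overnight in a hospital", "Experienced a problem that resulted in a severe or permanent disability" and "Experienced a life threatening injury or event". DSMP 5.2.1, Table 1 (follow-up health surveys) repeats the stem under the statement "All participants will be queried for Serious Adverse Events".

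The definitions that the question serves are wider. DSMP 6.1.1 counts any undesirable event as an adverse event, whether or not it is related to the study. DSMP 6.2.1 defines seriousness by outcome (death, life-threatening condition, hospitalization, disability) and does not separate psychiatric from medical causes.

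On surveillance, protocol 3.3.3 provides for adverse event monitoring at every intervention session, and section 5.1.2 gives nine weekly sessions in the RCT. Under the same section, Usual Care participants only complete follow-up surveys. DSMP 6 lists three sources of event information: participants contacting staff, survey queries and staff observation. DSMP 7.5 has serious adverse events presented by group in the closed report.

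**The concern.** Elsewhere the plan treats the mental and the medical as separate domains. The checklist just described says physical or mental. DSMP 5.2 lists the natural history of mental health conditions apart from that of pain. The screening row of DSMP Table 1 has its own term, "Hospitalization for a severe mental illness-related issue in the past 6 months". A respondent who has just read about physical or mental symptoms and then meets the word medical alone may infer a contrast and answer no about a psychiatric admission.

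Psychiatric events matter to this trial's safety case. The non-physical risks that the plan names for RAMP are emotional, and only severe, poorly controlled psychiatric or substance use disorder is excluded (section 5.4.2), so other comorbidity remains in the sample. A missed event in RAMP has a second scheduled chance of detection, at a session. In Usual Care it has none. At stake are the completeness of serious-event counts in both arms and the fairness of the by-group comparison that the DSMB sees.

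**Working it through.** The documents give no event rate or survey sensitivity, so there is no figure of the plan's to reproduce. The check is a comparison of texts, followed by an illustration on assumed inputs.

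**Text comparison**

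1. Stem: the noun phrase is limited to a medical issue or an event, in both places where the question appears. No mental health term is used.
2. Branches: overnight stay, disability and life-threatening event are outcomes, and none is limited to a physical cause. A psychiatric admission or a suicide attempt can be answered yes. The defect is ambiguity.
3. Checklist: it covers mental symptoms in both arms but does not ask about seriousness. Except for the Other item, free text opens only when the participant says that the symptom was related to the study. Someone who ticks sadness and answers unrelated is not asked about an admission, although DSMP 6.1.1 counts unrelated events.
4. Passive routes (telephone line, email, encouragement to report): open to both arms, but they depend on the participant volunteering.
5. Electronic health record: not among the three sources in DSMP 6, although section 5.8 uses record data for other purposes.

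**Illustration (assumed inputs)**

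- From the documents: n = 250 per arm (500 randomized; the equal split follows from 200 per arm among 400 completers), and survey response q = 0.80 (up to 20% attrition, section 5.8).
- Assumed: true psychiatric serious-event rate p = 2% in both arms, so 250 × 0.02 = 5 events per arm; stem sensitivity s = 0.5 to 1.0; proportion c = 0 to 0.6 of survey-missed RAMP events caught at sessions; passive reporting ignored.

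Expected captured events:

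- Usual Care = n·p·q·s
- RAMP = n·p·[1 − (1 − q·s)(1 − c)]

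For example, with s = 0.5 and c = 0.3, Usual Care = 5 × 0.8 × 0.5 = 2.0 and RAMP = 5 × [1 − 0.6 × 0.7] = 2.9, a ratio of 1.45.

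| s | Usual Care | RAMP, c = 0 / 0.3 / 0.6 | Ratio |
|---|---|---|---|
| 0.50 | 2.0 | 2.0 / 2.9 / 3.8 | 1.0 / 1.45 / 1.9 |
| 0.75 | 3.0 | 3.0 / 3.6 / 4.2 | 1.0 / 1.2 / 1.4 |
| 1.00 | 4.0 | 4.0 / 4.3 / 4.6 | 1.0 / 1.08 / 1.15 |

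At p = 4% the counts double and the ratios do not change.

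The column c = 0.6 is generous. Nine weekly sessions cover about 9 of the 26 weeks to the 6-month survey, so with events spread evenly c cannot exceed 9/26 = 0.35. At c = 0.35 and s = 0.5, RAMP = 5 × [1 − 0.6 × 0.65] = 3.05, a ratio of 1.53. At s = 1, RAMP = 5 × [1 − 0.2 × 0.65] = 4.35, a ratio of 1.09.

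Any imbalance therefore has two causes, the wording and the extra contact. Better wording removes only the first.

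**The case against.** The strongest reply is that a plain reading already takes in psychiatric events. The stem adds the word event, the branches use their own nouns, and they match the seriousness criteria other than death. The survey is framed, before and after, by text on emotional and mental wellbeing (DSMP Table 1). Usual Care participants have a staffed telephone line and email address, and are encouraged to report. The consequence is also limited: the likely distortion under-counts Usual Care, so the comparison would make RAMP look worse and would not hide a RAMP harm; DSMP 6.4 sets no count threshold for halting; no between-arm test of serious events is specified; and the primary outcome is untouched.

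Much of this stands. A reader might infer that the question excludes psychiatric events, or that Usual Care has no other way to report them. The documents support neither. A reader might also infer that suicidality, which DSMP 5.2.1 gives as an example in "a participant is at risk of experiencing a serious adverse event (e.g., suicidality", is lost because of the stem. That does not follow either: suicidality with no hospital stay, disability or life-threatening event meets none of the DSMP 6.2.1 criteria, and a reworded stem with the same three branches would not capture it.

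What the reply does not answer is the ambiguity itself. The framing text is general crisis-line language and does not say that medical includes psychiatric. The checklist asks nothing about seriousness. Passive reporting is not a scheduled query.

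**Conclusion.** The point holds as a matter of clarity and even ascertainment. The scheduled serious-event question is narrower in wording than the definitions it serves, and a wrong no is possible for a psychiatric or substance-use admission. Because the survey is the only scheduled route in Usual Care and RAMP has nine monitored sessions as well, such misses could be somewhat more frequent in Usual Care in the by-group tables.

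The size is unknown. The event rate, stem sensitivity and session catch used above are assumptions, and no specific pair of observed counts can be defended from the documents. A reader might attribute any imbalance wholly to the wording, but part of it would remain with perfect wording because RAMP participants have more contact with staff. This is a cheap improvement to safety data. It does not threaten the trial's main conclusion.

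**What to change.** 1. In protocol 3.3.3 and DSMP 5.2.1, Table 1, change the stem to *a NEW or WORSENING medical or mental health issue or event*, and add to item (a), after the hospital stay, *(including for a mental health or substance use problem)*. Use the same wording in both arms.
2. In the by-group tables of DSMP 7.5, show survey-ascertained serious events, which are collected alike in both arms, separately from session-ascertained ones. This deals with the part of the imbalance that rewording cannot remove.
3. Separately, reconcile the suicidality example in DSMP 5.2.1 with the seriousness criteria in DSMP 6.2.1.

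The cost is a few words in the 3- and 6-month surveys and the DSMP table, an IRB wording amendment, and one extra split in the safety tables. The one drawback is that surveys already returned carry the present stem, so the survey version must be recorded with each response.

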4.0 Objectives and Endpoints

This project addresses the significant challenge of implementing effective, non-opioid interventions for chronic pain management in rural and remote dwelling Veteran patients.^{1,2} The Veterans Healthcare Administration (VA) is the nation's largest integrated healthcare system and serves an estimated 2.7 million rural Veterans.³ Rural Veterans experience a disproportionate share of the national pain burden, with more chronicity, opioid harms, comorbid mental health conditions and substance abuse, compared to non-rural Veterans and non-Veterans.^{4,5} Rural Veterans are also less likely to receive comprehensive and specialty pain care,^{6,7} are prescribed over 30% more opioids,⁸ and are less likely to use self-management interventions for pain than non-rural Veterans.^{7,9} Importantly, rural women and minority Veterans living in rural areas experience additional challenges that prevent equitable pain care.
6,10-17

Pain is a complex biophysical, psychological and social (BPS) condition^{10,11} and there is a growing evidence base to support several complementary and integrative health (CIH) approaches to manage chronic pain in a more holistic way.¹⁸⁻²⁰ While the VA has become a leader in advancing CIH through its Whole Health Initiative, there remain many barriers, especially for rural patients. This includes lack of awareness/knowledge about CIH, shortage of availability and accessibility of CIH/Whole Health pain care services, and absence of the necessary support to successfully engage in CIH self-management.^{3,21-24}

Our long-term objective is to improve pain management and reduce opioid use among rural patients in the VA. Our multidisciplinary team has co-designed, with multiple levels of advisors, an innovative telehealth/virtual intervention that builds upon our team's previous research.^{6,25-32} The Reaching Rural Veterans: Applying Mind-Body Skills for Pain Using a Whole Health Telehealth Intervention (**RAMP**) project strategically coalesces multiple evidence based CIH self-management strategies to address Veterans' BPS needs and overcome existing barriers. Comprised of mindfulness training, pain education, pain specific exercises, and cognitive behavioral strategies, the program is cohesive and scalable. RAMP is a 9-week program comprised of weekly group sessions with pre-recorded expert-led education videos, mind-body

skill training and practice, and facilitated discussions. To ensure long-term sustainability, we will collaborate with advisors including Veteran patients and an established network of VA health system partners including the Office of Rural Health; the Office of Pain Management, Opioid Safety, & Prescription Drug Monitoring (which has been investing in telehealth for pain); and the Office of Patient Centered Care and Cultural Transformation. We will also cultivate new community partnerships with the VA's Community-Based Outpatient Clinics (CBOCs) and local and national Veteran organizations. There are two phases to the project, a UG3 and UH3.

The specific aims for the UG3/Phase 1 and UH3/Phase 2 of the project are:

UG3/Phase 1 Aim 1: We will conduct **advisor engagement activities** including identifying and developing new community partnerships and using mixed methods data collection from multiple levels of advisors (n=35-50 patients, community partners, VA healthcare system leaders and staff), guided by the established REAIM/PRISM framework, to learn about key factors that can affect long-term adoption.

UG3/Phase 1 Aim 2: We will conduct a **feasibility study** of 40 rural VA patients with chronic pain to assess the feasibility of delivering RAMP (pilot) in terms of recruitment and engagement, intervention fidelity and adherence, data collection, and other key metrics.

UH3/Phase 2 Aim 1: We will conduct a **randomized hybrid type 2 effectiveness-implementation pragmatic clinical trial (RCT)** of RAMP compared to Usual Care, randomizing 500 rural VA patients from the VA healthcare system, oversampling female and racial/ethnic minority patients. The aim is to assess the relative effectiveness of RAMP in rural VA patients in terms of pain interference (**primary outcome**) at 3 and 6 months and **secondary outcomes** of opioid use and other HEAL recommended outcomes. We will ask intervention participants about their experience with the RAMP program. We will also perform additional exploratory analyses of women and minority Veterans' primary and secondary outcomes.

UH3/Phase 2 Aim 2: We will work iteratively with multiple levels of advisors (n=35-50 patients, community partners, VA healthcare system leaders and staff) to evaluate intervention implementation strategies used in the trial and adapt these strategies to scale up RAMP within the national VA healthcare system. This will include:

- a. Conducting mixed-methods assessments of advisor and randomized trial participant views of implementation related barriers and facilitators, resource needs, and other RE-AIM/PRISM domains.
- b. Working with advisors to co-create additional plausible strategies for overcoming barriers to implementation of RAMP in the national VA healthcare system.
- c. Conducting budget impact analyses using models informed by advisor views to inform future decision making.

5.0 Study Procedures

5.1 Overall Design

This is a two-phase study with a UG3 phase in years 1-2 and a UH3 phase in years 3-5 (see Figure 1).

5.1.1 Advisor Engagement

We will ask the stakeholders to complete iterative qualitative assessments and use participatory research methods to collaborate and problem solve for implementing RAMP given the internal and external contexts that may be affecting the VA and Whole Health System initiatives at the time. Data collection will include a combination of primary data collection via surveys, qualitative interviews, and focus groups. Meeting times will be agreed upon ahead of time between facilitators and stakeholders. All reasonable efforts will be made to work with each stakeholders' schedule and preference for meeting. Additional contact reasons, particularly towards the end of the study, may include alerting advisors to study results and other research participation opportunities.

Advisor Population Characteristics

This study will include Veteran, Community and VA stakeholders/partners who will help evaluate intervention implementation strategies within the trial and adapt these strategies to scale out Reaching Rural Veterans: Applying Mind-Body Skills for Pain Using a Whole Health Telehealth Intervention (RAMP) to rural-dwelling patients in the national VA healthcare system. All advisors will be 18 years or older. We plan to specifically include advisors from diverse backgrounds (e.g., in terms of race/ethnicity, sex).

Advisors involved in our study may require additional protection, either because they are from under-supported populations, minority populations, are women, and/or are employees of the VA. All study subjects are expected to be 18 years of age or older (no children will be included). We will follow all required protocols when working with VA employees as study participants, including communication with employee unions. Because our long-term goal is to provide evidence-based pain management to the many rural-dwelling patients in the VA healthcare system with chronic pain and under-supported populations are disproportionately affected by chronic pain, it is critical we include advisors from such populations in our study. In addition, because the program delivery and success are dependent on VA employees, they are also crucial to our study.

